
Severe Acute Exacerbation of Hepatitis B in Patients Coinfected with HIV-1 and HBV
	
Severe acute exacerbations of hepatitis B (e.g., liver decompensation and liver failure) have been reported in patients who are coinfecting with HIV-1 and HBV and have discontinued products containing FTC and/or tenofovir disoproxil fumarate (TDF) and may occur with discontinuation of BIK.
	
 • All chronic HBV infected patients (HBsAg+ are excluded from study as are those who are negative for anti-HBs but positive for anti-HBc (negative HBsAg status) AND positive for HBV DNA are also excluded from study. • Patients coinfecting with HIV-1 and HBV who discontinue BIK should be closely monitored with both clinical and laboratory follow-up for at least several months after stopping treatment. If appropriate, anti-hepatitis B therapy may be warranted, especially in patients with advanced liver disease or cirrhosis, since post-treatment exacerbation of hepatitis may lead to hepatic decompensation and liver failure.

Potential Risk of Clinical Significance	Summary of Data/Rationale for Risk	Mitigation Strategy

Risk of Adverse Reactions or Loss of Virologic Response Due to Drug Interactions
	
The concomitant use of BIK with certain other drugs may result in known or potentially significant drug interactions, some of which may lead to (See Section 6.11.1):
 
 • Loss of therapeutic effect of BIK and possible development of resistance. • Possible clinically significant adverse reactions from greater exposures of concomitant drugs. 
Consider the potential for drug interactions prior to and during BIK therapy;
	
 • See BIK product information for steps to prevent or manage these possible and known significant drug interactions, including dosing recommendations. • Monitor for the adverse reactions associated with the concomitant drugs.

New Onset or Worsening Renal Impairment
	
Renal impairment, including cases of acute renal failure and Fanconi syndrome (renal tubular injury with severe hypophosphatemia), has been reported with the use of tenofovir prodrugs in both animal toxicology studies and human trials. In clinical trials of BIK, there have been no cases of Fanconi syndrome or Proximal Renal Tubulopathy (PRT). In clinical trials of BIK in participants with no antiretroviral treatment history with eGFRs greater than 30 mL per minute, and in virologically suppressed participants switched to BIK with eGFRs greater than 50 mL per minute, renal serious adverse events were encountered in less than 1% of participants treated with BIK through Week 48 (see Biktarvy Product Information, 2019).
 
Patients taking tenofovir prodrugs who have
	
 • During treatment with BIK, assess serum creatinine, estimated creatinine clearance, urine glucose and urine protein in all patients as clinically appropriate. • In patients with chronic kidney disease assess serum phosphorus. • Discontinue BIK in patients who develop clinically significant decreases in renal function or evidence of Fanconi syndrome.

Potential Risk of Clinical Significance	Summary of Data/Rationale for Risk	Mitigation Strategy
	
impaired renal function and those taking nephrotoxic agents including non-steroidal anti-inflammatory drugs are at increased risk of developing renal-related adverse reactions.
 
Prior to or when initiating BIK, and during treatment with BIK, assess serum creatinine, estimated creatinine clearance, urine glucose and urine protein in all patients as clinically appropriate. In patients with chronic kidney disease, also assess serum phosphorus. Discontinue BIK in patients who develop clinically significant decreases in renal function or evidence of Fanconi syndrome.
	
Lactic Acidosis/Severe Hepatomegaly with Steatosis	
Lactic acidosis and severe hepatomegaly with steatosis, including fatal cases, have been reported with the use of nucleoside analogs, including emtricitabine, a component of BIK, and tenofovir DF, another prodrug of tenofovir, alone or in combination with other antiretrovirals.
	
 • Treatment with BIK should be suspended in any patient who develops clinical or laboratory findings suggestive of lactic acidosis or pronounced hepatotoxicity (which may include hepatomegaly and steatosis even in the absence of marked transaminase elevations).

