	
Eosinophilia and Systemic Symptoms (DRESS), with oral RPV containing regimens. While some skin reactions were accompanied by constitutional symptoms such as fever, other skin reactions were associated with organ dysfunctions, including elevations in hepatic serum biochemistries.
	
allowed to continue treatment, depending on the clinical judgment of the investigator.
 
 • All participants experiencing a Grade 3 or 4 rash should discontinue their ARV medication (study medication) and be withdrawn from the study. • All rash events should be assessed with special attention to systemic symptoms, laboratory abnormalities, or mucosal involvement. Close clinical follow-up, including follow-up of laboratory abnormalities, and appropriate medical intervention, including referral to dermatologist as appropriate, should be instituted for these events; daily follow-up is recommended for 5 days from the onset of the event to monitor for progression of the event. See Section 8.3.11.9 for additional guidance on management of rash events.

Potential Risk of Clinical Significance	Summary of Data/Rationale for Risk	Mitigation Strategy

Development of Resistance
	
Residual concentrations of RPV LA can remain in the systemic circulation of participants who stopped treatment (e.g., for tolerability issues or treatment failure) for prolonged periods (months to more than a year, in some participants, McGowan, 2016).
 
Participants discontinuing a LA regimen may be at risk for developing resistance to RPV many weeks after discontinuing injectable therapy.
	
 • After participants stop RPV LA, Oral HAART regimens will be prescribed within 8 weeks after the last Q2M dose and following consultation with the medical monitor. This would be anticipated to result in rapid resuppression of HIV-1 RNA thus minimizing the risk of emergent resistance • The Sponsor will continue to monitor participants in this study who discontinue a LA regimen for any reason for a minimum of 52 weeks from the time of the last LA administration.

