Participants must be discontinued from study treatment for any of the following reasons:

- Participants who are not eligible to continue into the Maintenance Phase.
- Participants who are not eligible, or do not wish to continue on to the Extension Phase.
- Virologic withdrawal criteria as specified in Section 7.1.6 are met;
- Participant requires substitution of ART;
- Participant requires substitution or dose reduction of CAB LA or RPV LA (oral bridging supply and potential for a second loading dose may be permissible following discussion with the Medical Monitor).
- Liver toxicity where stopping criteria are met and no compelling alternate cause is identified (see Section 7.1.2);
- Renal toxicity is met and no compelling alternate cause is identified;
- QT interval (QTc) interval >550 msec from three or more tracings separated by at least 5 minutes and considered causally related to IP.
- Grade 4 clinical AE considered causally related to study drug;
- Participant has a Grade 3 or higher rash or Grade 2 rash with evidence of systemic involvement and no compelling alternative cause is identified
- Pregnancy (intrauterine), regardless of termination status of pregnancy (for participants on BIK only) Participant withdrew consent

Efficacy data for participants withdrawing from the study will be considered evaluable up to the point at which they are withdrawn using the same criteria for evaluability as for participants who complete the study.

Safety data for all participants who receive any amount of study drug, including participants who withdraw from the study, will be included in evaluations of safety.

All data from the Withdrawal visit will be recorded, as they comprise an essential evaluation that should be done prior to discharging any participant from the study.

The following actions must be taken in relation to a participant who fails to attend the clinic for a required study visit:

- a. The site must attempt to contact the participant and re-schedule the missed visit as soon as possible.
- b. The site must counsel the participant on the importance of maintaining the assigned visit schedule and ascertain whether or not the participant wishes to and/or should continue in the study.
- c. In cases where the participant is deemed 'lost to follow up', the investigator or designee must make every effort to regain contact with the participant (where possible, 3 telephone calls and if necessary, a certified letter to the participant's

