8.3.11.9. Rash Without ABC HSR Symptoms

Including serious skin reactions such as Stevens-Johnson Syndrome, Toxic Epidermal Necrolysis, Erythema Multiforme or rash with significant liver dysfunction.

Participants should be instructed to contact the Investigator as soon as possible if they develop a rash on study.

CAB is an analogue of DTG and mild to moderate rash is an expected adverse reaction for DTG-containing ART. Episodes generally occur within the first ten weeks of treatment, rarely require interruptions or discontinuations of therapy and tend to resolve within two to three weeks. No instances of serious skin reaction, including Stevens-Johnson syndrome (SJS), toxic epidermal necrolysis (TEN) and erythema multiforme, have been reported for DTG in clinical trials. For further characterization of HSR and rash observed with DTG-containing ART, please see the current version of the IB [GlaxoSmithKline Document Number [RPS-CLIN-004375](#), 2021].

Rash is an adverse drug reaction (ADR) for RPV. In clinical trials, most rashes emerged during the first 4 weeks of treatment, were transient, and usually mild (Grade 1) to moderate (Grade 2). There were no Grade 4 rashes, and none were serious. Treatment-related Grade 3 rash was reported in 0.1% of participants in the RPV group. Treatment-related rash led to permanent discontinuation in 0.1% of participants in the RPV group. No cases of erythema multiforme, SJS or TEN have been reported during clinical development of RPV.

Participants with an isolated Grade 1 rash may continue study drug at the Investigator's discretion. The participant should be advised to contact the Investigator immediately if there is any worsening of the rash, if any systemic signs or symptoms appear, or if mucosal involvement develops.

Participants may continue study drug for an isolated Grade 2 rash. However, study drug (and all other concurrent medication(s) suspected in the Investigators causality assessment) should be permanently discontinued for any Grade ≥ 2 rash that is associated with an increase in ALT. The participant should be advised to contact the physician immediately if rash fails to resolve (after more than two weeks), if there is any worsening of the rash, if any systemic signs or allergic symptoms develop, or if mucosal involvement develops.

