Participants should permanently discontinue study drug [and all other concurrent medication(s) suspected in the Investigators causality assessment] for an isolated Grade 3 or 4 rash, except where the etiology of the rash has been definitively diagnosed as NOT attributable to study drug (see below), and the participant should be withdrawn from the study. Participants should be treated as clinically appropriate and followed until resolution of the AE. Every effort should be made to collect as much information as possible about the evolution of the event and any relationship with potentially related medical events (e.g., viral infection) or start of concomitant medication.

The rash and any associated symptoms should be reported as adverse events and appropriate toxicity ratings should be used to grade the events (based on DAIDS toxicity gradings – see Section 10.4).

However, if the etiology of the rash has been definitively diagnosed as being unrelated to study drug and due to a specific medical event or a concomitant infection or a concomitant non-study medication, routine management should be performed, and documentation of the diagnosis provided. In this situation, the study drug should be continued.

Participants in the Follow-Up Phase who are receiving ABC as part of their regimen should be evaluated for the possibility of a clinically suspected ABC HSR and managed appropriately as outlined in the local prescribing information for ABC.

Any rash that is possibly related to study drug, and is present between Day 1 and The Month 1b visit for participants in the Oral Lead-in Phase, must be discussed with the Medical Monitor prior to initiation of CAB LA or RPV LA.

Any participant receiving at least one dose of CAB LA and /or RPV LA who discontinue IP / Withdraw will initiate treatment with HAART and enter the LTFU Phase for 52 weeks of follow-up.

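### Sections 2.3.1, 7.1 and 8.3.11.9 give conflicting stopping instructions for Grade 3 or 4 rash not due to study drug, with a narrower mismatch at Grade 2

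*Protocol*

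**What the plan says.** Three places in the protocol tell a site what to do about rash.

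- **Section 2.3.1, RPV LA risk table, Rash row (mitigation column).** Participants with Grade 1 or 2 rash are "allowed to continue treatment, depending on the clinical judgment of the investigator". At the higher grades the text reads: "All participants experiencing a Grade 3 or 4 rash should discontinue their ARV medication (study medication) and be withdrawn from the study". The row closes with a pointer: "See Section 8.3.11.9 for additional guidance on management of rash events".
- **Section 7.1, list of reasons for which study treatment must be discontinued.** The entry is: "Participant has a Grade 3 or higher rash or Grade 2 rash with evidence of systemic involvement and no compelling alternative cause is identified".
- **Section 8.3.11.9.** At Grade 2: "Participants may continue study drug for an isolated Grade 2 rash". Permanent discontinuation is nevertheless called for at Grade 2 or above for a "rash that is associated with an increase in ALT". An isolated Grade 3 or 4 rash leads to permanent discontinuation and withdrawal, "except where the etiology of the rash has been definitively diagnosed as NOT attributable to study drug (see below"). A later paragraph deals with rash definitively diagnosed as unrelated to study drug and says: "In this situation, the study drug should be continued".

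Two general toxicity sections also bear on this. Section 8.3.10.3 (Grade 3) lets dosing continue on compelling evidence of a non-drug cause, after discussion with the Medical Monitor. If the event is related or possibly related, drug is withheld and may restart once the event is Grade 2 or lower. Section 8.3.10.4 (Grade 4) requires permanent discontinuation unless there is compelling evidence of no causal relation and the Medical Monitor assents.

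**The concern.** The three sections do not apply the same test for a cause other than study drug. Section 2.3.1 has no such test, 7.1 asks for a compelling alternative, and 8.3.11.9 asks for a definitive diagnosis. For some rashes a site cannot follow all three, although Section 4.1 says that waivers and exemptions are not allowed.

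This affects participants first. For someone on the injections, stopping means switching to oral HAART and entering 52 weeks of long-term follow-up (Section 4.1.4), and Section 2.3.1 itself warns of resistance after stopping. It also reaches the data. The proportion discontinuing treatment because of AEs is a listed safety endpoint (Section 3), and discontinuation counts as failure in the key secondary analysis of HIV-1 RNA below 50 c/mL (Section 4.1). Whether a given rash becomes a discontinuation should not depend on which section the site happens to read.

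**Working it through.** The plan states no figure to reproduce. The check is to take one rash at a time and read off what each section requires. I read the alternative-cause clause in 7.1 as qualifying both its Grade 3 and its Grade 2 limb.

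| Case | 2.3.1 | 7.1 | 8.3.11.9 |
|---|---|---|---|
| A. Grade 3/4, no other cause found | stop, withdraw | must stop | stop permanently, withdraw |
| B. Grade 3/4, other cause compelling but not definitive | stop, withdraw | stop not required | stop permanently, withdraw |
| C. Grade 3/4, other cause definitively diagnosed | stop, withdraw | stop not required | continue |
| D. Grade 2, isolated | investigator judgement | not listed | may continue |
| E. Grade 2, systemic involvement, no compelling other cause | investigator judgement | must stop | continuation allowed only if isolated; stop stated only for ALT rise |
| F. Grade 2, ALT rise, other cause compelling but not definitive | investigator judgement | stop not required | stop permanently |
| G. Grade 2, ALT rise, other cause definitively diagnosed | investigator judgement | stop not required | ALT sentence has no exception; the later unrelated-cause paragraph probably means continue |

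**Grade 3/4.** Case A agrees throughout. Case C is a direct contradiction, since 2.3.1 covers everyone and 8.3.11.9 gives the opposite instruction. Case B shows that the disagreement is not confined to the risk table: 7.1 and 8.3.11.9, both operative sections, part company when the other cause is compelling but unproven. If the clause in 7.1 were instead read as qualifying only Grade 2, 7.1 would also stop in case C and the conflict with 8.3.11.9 would be sharper.

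**Grade 2.** Case D is consistent. The remaining mismatch is in E (judgement in 2.3.1, mandatory stop in 7.1) and F (no required stop in 7.1, permanent stop in 8.3.11.9). Case G can probably be resolved within 8.3.11.9.

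**General rules.** Sections 8.3.10.3 and 8.3.10.4 use compelling evidence, which is closer to 7.1 than to 8.3.11.9. Section 8.3.10.3 also allows restart after a related or possibly related Grade 3 event, whereas 8.3.11.9 makes discontinuation permanent for rash.

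**Size.** Inputs are the arm sizes in Table 7 (436 and 218). One participant moves an arm's AE-discontinuation proportion by:

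- CAB LA + RPV LA: 1/436 = 0.0023, or 0.23 percentage point
- BIK: 1/218 = 0.0046, or 0.46 percentage point

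These are the weights of one event, not estimates of how many will occur. The only rash rate of the relevant grade is the 0.1% in 8.3.11.9 for treatment-related Grade 3 rash with RPV. Treatment-related rash is case A, where the three sections agree, so that rate neither measures nor bounds cases B and C.

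**The case against.** The best defence is that 2.3.1 is a risk summary, not an operating instruction. Its sentence says should rather than must, it sits in a mitigation column, and the same cell sends the reader to 8.3.11.9. The operative sections, including 8.3.10.3 and 8.3.10.4, all provide for a cause other than study drug, and only the summary omits it. This has weight, but it does not settle the matter. The sentence is framed as a rule for everyone, the pointer offers 8.3.11.9 as additional guidance rather than as the governing text, and no section says which prevails. It also leaves case B untouched.

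A second defence is central control. Section 6.9 requires dose interruption and resumption decisions to be discussed with the Medical Monitor in advance, and 8.3.10.3 and 8.3.10.4 require that discussion before dosing continues through an event judged unrelated. A reader might infer that the same rash would mean compulsory withdrawal at one site and continuation at another. The document does not support putting it that strongly, because the compulsory list in 7.1 already has an exception and the Medical Monitor limits divergence between sites. The Medical Monitor, however, works from the same conflicting text.

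A reader might also infer three contradictory rules for Grade 2. That goes too far. The rules are mostly layered: a permission resting on judgement, with attention to systemic symptoms and laboratory abnormalities in the same table row, then a limit to isolated rash, then specific stops. An ALT rise may itself be read as systemic involvement. Cases E and F are what remains.

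**Conclusion.** The rash rules are wrong as written for Grade 3 or 4 rash not due to study drug. Section 2.3.1 contradicts 8.3.11.9 when another cause is definitive, and 7.1 differs from 8.3.11.9 when it is compelling but not definitive. The Grade 2 mismatch is real but narrow.

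The number of affected participants is unknown, because the document gives no rate for such rash. It is likely small, and each one in the long-acting arm is worth 0.23 percentage point of AE discontinuation, an endpoint that Section 9.4.2 summarises without a hypothesis test. No effect on the primary non-inferiority conclusion is claimed or shown.

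Because the unconditional sentence sits under the RPV LA heading, a reader might infer a bias between arms in AE discontinuation. That is a possibility on a literal reading only; nothing in the document shows that it would occur or how large it would be.

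**What to change.** The sponsor must reconcile Sections 2.3.1, 7.1 and 8.3.11.9 so that each rash grade has one rule and a single attribution standard for a cause other than study drug. The rule should cover explicitly the Grade 2 cases with systemic involvement and with an ALT rise. Sections 8.3.10.3 and 8.3.10.4 should be checked against it. One section should be named as governing, and the others should refer to it rather than restate it. This review takes no view on which clinical rule or standard is right.

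The cost is protocol wording and a notice to sites. Sample size, visit schedule and planned analyses do not change.

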2.3.2. Benefit Assessment

The antiviral activity against HIV-1 of CAB has been well established through Phase 2a, Phase 2b and Phase 3 studies. RPV, both oral (marketed as EDURANT) and LA, is an established antiviral agent against HIV-1 in treatment naive patients, with long term durability (>96 weeks in Phase 3 and >240 weeks in Phase IIb).

Participants receiving CAB LA + RPV LA are anticipated to benefit from maintenance of virological suppression using LA agents. The regimen provides an alternative to daily oral treatment with an extended dosing option, avoiding drug-drug and drug-food interactions within the GI tract with IM dosing. Participants randomized to receive CAB LA+ RPV LA Q2M dosing will not need to take concomitant daily oral therapy. Adherence in these participants is expected to be improved and will be directly observed during IM injections. Efficacy of the two-drug regimen, as oral agents, has been demonstrated through Week 312 of the LAI116482 study, and as IM agents, has been demonstrated through Week 160 of the ongoing 200056 study and Week 48 of the ongoing ATLAS 2M study. The reduction in ART, and the discontinuation of NRTIs, may offer long term safety and tolerability benefits in these participants.

2.3.3. Overall Benefit: Risk Conclusion

Taking into account the measures taken to minimize risk to participants participating in this study, the potential risks identified in association with CAB LA and RPV LA Q2M and BIK regimens, and the study as a whole are justified by the anticipated benefits that may be afforded to treatment-experienced patients with HIV-1 infection.

3. OBJECTIVES AND ENDPOINTS

Objectives	Endpoints
Primary	
To demonstrate the non-inferior antiviral activity of CAB LA + RPV LA every two months compared to a BIK single tablet regimen administered once daily over 12 months in suppressed HIV-1 infected antiretroviral therapy (ART)-experienced participants	Proportion of participants with plasma HIV-RNA greater than or equal to 50 copies/mL as per Food and Drug Administration (FDA) Snapshot algorithm at Month 12 (OLI and BIK)/Month 11 (D2I) (Intent-to-Treat Exposed [ITT-E] population)
Secondary	
To demonstrate the antiviral and immunologic response with the use of CAB LA + RPV LA every 2 months compared to a BIK single tablet regimen administered once daily	Proportion of participants with plasma HIV-1 RNA <50 c/mL (c/mL) at Month 6 and Month 12 (OLI and BIK)/Month 5 and Month 11 (D2I) using the FDA Snapshot algorithm (Intent-to-Treat Exposed [ITT-E] population)

Objectives	Endpoints
	
Proportion of participants with protocol-defined confirmed virologic failure (CVF) through Month 6 and Month 12 (OLI and BIK)/Month 5 and Month 11 (D2I).
 
Proportion of participants with HIV-RNA greater than or equal to 50 c/mL as per FDA Snapshot algorithm at Month 6, and Month 12 (OLI and BIK)/Month 5 and Month 11 (D2I)
 
Absolute values and changes from Baseline in viral load and CD4+ cell count over time including Month 6 and Month 12 (OLI and BIK)/Month 5 and Month 11 (D2I)

To assess viral resistance in participants experiencing protocol-defined confirmed virologic failure	Incidence of treatment emergent genotypic and phenotypic resistance to CAB, RPV, BIC, FTC, and TAF through Month 6 and Month 12 (OLI and BIK)/Month 5 and Month 11 (D2I).
To evaluate renal (in urine and blood) and bone (in blood) biomarkers in participants treated with CAB LA + RPV LA compared to BIK	Change from Baseline (Day 1) in renal and bone biomarkers at Months 6 and 12 (OLI and BIK)/Month 5 and Month 11 (D2I).
To evaluate Metabolic Syndrome for participants treated with CAB + RPV and BIK	Change from Baseline in proportions of participants with Metabolic syndrome at Months 6 and 12 (OLI and BIK)/Month 5 and Month 11 (D2I)
To evaluate insulin resistance in participants treated with CAB LA + RPV LA compared to BIK	Change from Baseline (Day 1) in homeostasis model of assessment-insulin resistance (HOMA-IR) at Months 6 and 12 (OLI and BIK)/Month 5 and Month 11 (D2I).
To assess preference for CAB LA + RPV LA administered every 2 months compared to a BIK single tablet regimen administered once daily	Preference for CAB LA + RPV LA every 2 months compared to a BIK single tablet regimen will be assessed using a preference questionnaire at Month 12 (OLI)/Month 11 (D2I) (or Withdrawal).

Objectives	Endpoints

To assess patient reported treatment satisfaction, and injection tolerability.
	
Change from baseline (Day 1) in total “treatment satisfaction” score, and individual item scores of the HIV Treatment Satisfaction Status Questionnaire (HIVTSQs) at Month 6 and Month 12 (OLI and BIK)/Month 5 and Month 11 (D2I), (or Withdrawal)
 
Change in treatment satisfaction over time using the HIV Treatment Satisfaction Change Questionnaire HIVTSQc total score and individual item scores at Month 12 (OLI and BIK)/Month 11 (D2I) (or Withdrawal).
 
Change from Month 2 in Dimension scores (“Acceptance of ISRs”, “Bother of ISRs”, “Leg movement”, “Sleep”) and individual item scores (assessing pain during injection, anxiety before and after injection, willingness to be injected in the future and overall satisfaction with mode of administration over time) will be assessed using the Perception of injection questionnaire (PIN) at Months 2, 6, and 12 (OLI)/Months 1, 5, 11 (D2I) (or Withdrawal)

Safety
	

To evaluate the safety and tolerability of CAB LA + RPV LA every 2 months compared to a BIK single tablet regimen administered once daily
	
Incidence and severity of AEs and laboratory abnormalities over time including Month 6 and Month 12 (OLI and BIK)/Month 5 and Month 11 (D2I).
 
Proportion of participants who discontinue treatment due to AEs over time including Month 6 and Month 12 (OLI and BIK)/Month 5 and Month 11 (D2I).
 
Change from Baseline in laboratory parameters over time including Month 6 and Month 12 (OLI and BIK)/Month 5 and Month 11 (D2I).

CCI

CCI

CCI

